**Figure 1: Study Design Flow Chart**

Adjunct treatment is planned to be 2-days (which includes a 12-hour taper).

Hours 24-36 should start with an infusion rate of 20mg/hr with dose adjustments allowed up to 45mg/hr.

Total subject participation is expected to be approximately 4 weeks.

### 3.2 Duration and Study Completion Definition

The subject's maximum duration of participation is expected to be approximately 4 weeks. It is anticipated the study will take 24 months to complete including approximately 18 months of subject enrollment.

The study completion date is defined as the date the final subject, across all sites, completes their final protocol-defined assessment. Please note that this includes the follow-up visit/contact, whichever is later. The study completion date is used to ascertain timing for posting and reporting of study results.

### 3.3 Sites and Regions

This multicenter study is to be conducted globally, with approximately 150 sites planned to participate.

## 4. STUDY POPULATION

Each subject/parent/guardian/legally authorized representative (LAR) must participate in the informed consent process and provide written informed consent/assent before any procedures specified in the protocol are performed. Consent/assent will be administered per the hospital's IRB/EC policy and may vary across sites, i.e., some sites may be able to consent/assent over the

phone or other communication methods. Consent/assent for subjects who are known to be at risk for SE may be obtained prior to a SE event. The period of time the pre-consent/assent is valid will be determined by each hospital's IRB/EC. However, reconsenting will be needed should the consent/assent be updated at any point during the study.

#### **4.1 Inclusion Criteria**

The subject will not be considered eligible for the study without meeting all the criteria below.

1. Subject, subject's parent, guardian, or LAR must provide signature of informed consent, and, once capable (per the investigator's hospital guidelines), there must be documentation of consent/assent by the subject indicating the subject is aware of the investigational nature of the study, is able and willing to participate in the study, and is aware of the required restrictions and procedures
2. Male or female subjects 12 years of age and older at the time of the first dose of study drug
3. Clinical and/or electrographic seizures defined as:
  - Documented clinical seizures (convulsive SE): greater than 5 minutes' duration prior to treatment with study drug (per ILAE)  
or
  - Electrographic criteria (one must apply):
    - 10 minutes of continuous seizure activity on EEG (per ILAE)
    - Intermittent electrographic seizure activity for more than 50% of the previous 60 minutes
    - If less than 60 minutes of EEG is available, then intermittent electrographic seizure activity must be present for greater than 50% of the available duration of the EEG AND the electrographic seizure activity must be at least 10 minutes when taken in aggregate
4. Subject on concurrent 2nd line IV AED therapy with fosphenytoin/phenytoin, valproic acid, levetiracetam, lacosamide, or brivaracetam for the management of the current episode of SE
5. BMI < 40 or, if not able to be calculated at screening, assessed by investigator as not morbidly obese

#### **4.2 Exclusion Criteria**

Subjects are excluded from the study if any of the following exclusion criteria are met.

1. Life expectancy of less than 24 hours
2. Anoxic brain injury as the primary cause of SE
3. Recent (< 24 hour) traumatic brain injury as the primary cause of SE

4. Administered anesthesia (3rd line treatment; e.g., midazolam, propofol, thiopental, pentobarbital, or ketamine) at adequate doses and duration for the treatment of the current episode of SE that required the subject to be hospitalized and 5 half-lives of the agent used has not elapsed
5. Subjects who are intubated for the administration of an IV anesthetic drug (a 3rd line treatment; e.g., midazolam, propofol, thiopental, pentobarbital, or ketamine) to treat SE; subjects who are intubated for airway protection are not excluded
6. Subjects known or suspected to be pregnant upon screening
7. To the best knowledge of the investigator, has allergy to progesterone or allopregnanolone medications/supplements or has previously received ganaxolone or exogenous allopregnanolone
8. If renal impairment is suspected (eGFR  $\leq$  45 mL/min) or subject is currently on dialysis; if decision is made to start dialysis during study participation, subject is not excluded.
9. To the best knowledge of the investigator, subject has hepatic insufficiency at screening, for example alanine transferase or aspartate transferase level more than 5 times the upper limit of normal (ULN), or total bilirubin more than 2 times ULN at the screening visit
10. Subjects with a durable medical care agreement that would not allow hospital to administer their standard of care for treatment of SE
11. Subjects on an investigational drug that is not recommended by treatment guidelines are required to have a reasonable expectation that the investigational study drug has been cleared from their system, that is, that five half-lives have elapsed
12. Subjects who have a history or evidence of a medical condition that, in the investigator's judgment, would expose subject to an undue risk of a significant adverse event or interfere with assessments of safety or efficacy during the course of the study

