**Table 1: Schedule of Assessments**

Periods	Screening a	Treatment			Follow-up b		ET	
Visit/Timepoint or Duration	Prior to study drug initiation	Dosing		Taper	Study Drug Discontinuation without Taper	In-patient Follow-up	Weekly follow-up (Week 2, 3, & 4)	Early Termination
	Day -1 to Day 1 Pre-dose through screening	Day 1 Study Drug Initiation 0 hours through 24 hours post study drug initiation	Day 2 24 hours through 36 hours post study drug initiation	Day 2 12-hours Starts at 36-hours post study drug initiation	Collected prior to or as close to study drug discontinuation as possible	Day 3 Or Starts as soon as study drug administration ends, lasts 24 hours	7 ±3, 14 ±3, and 21 ±3 days post last visit	Collected prior to or as close to study drug discontinuation as possible
AEs/SAEs u		✓	✓	✓	✓	✓	✓	✓
Concomitant medication u	✓	✓	✓	✓	✓	✓	✓	✓

ET, Early Termination; ECG, electrocardiogram; WCBP, women of childbearing potential; EEG, electroencephalograms; AE, adverse event; SAE, serious AE.

a. The screening period is from the time parent/guardian/LAR consent is obtained to immediately prior to study drug initiation.

b. The planned duration of follow-up will be 24 hours after study drug administration is stopped (called the in-patient follow-up day) and weekly for an additional 3 weeks. For Weeks 2, 3, and 4 the follow-up can be performed as an in-patient visit if the subject is still in the hospital or, if the subject has been discharged, as a telephone call. Attempts should be made to have discharged subjects return for one of the follow-up visits for clinical laboratory sample collection. The follow-up visit window is 7 ±3, 14 ±3, and 21 ±3 days.

c. Demography and medical history will ideally be collected prior to study drug initiation but can be collected whenever feasible before the end of study drug taper.

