h. Clinical labs, hematology, serum chemistry (including creatinine, blood urea nitrogen, and estimated glomerular filtration rate calculation) and concomitant AED levels (fosphenytoin/phenytoin, valproic acid, levetiracetam, lacosamide, or brivaracetam, if available) and Urinalysis (including urine protein, albumin, and microscopic examination) should be collected pre-dose (screening), if available, or within 2 hours of study drug initiation, at 24- and 36- hours (+/- 1-hour) after study drug initiation. Collect at the time of study drug discontinuation, either at the end of the study drug taper or if the study drug administration is stopped without a taper and 24-hours (+/- 1-hour) after study drug discontinuation. Collect at one of the weekly follow-up visits (week 2, 3, or 4) for subjects in-house and if possible, for subjects who have been discharged. If possible, for subjects who early terminate from the study, collect at the time early termination is being considered and as close as possible to the end of the study drug administration. After the initial SE cessation, AED levels should be collected at time of first instance of seizure activity or SE relapse. Between study drug initiation and the in-patient follow-up day, where possible, collect AED levels if the decision is made to intubate the subject and for any serious adverse event (related or not related). Collect clinical labs, AEDs and urinalysis any time, if medically indicated, per investigator's judgment.

i. Drugs of abuse (urine or serum), including alcohol testing, and pregnancy test (urine or serum) for women who are of childbearing potential, should be collected pre-dose (screening). If not possible to collect pre-dose, collect as soon as possible after start of study drug infusion. Enrollment is not contingent upon results. However, if a subject has a positive test result, it will be at the investigator's discretion to weigh the risks versus benefits for the subject's continued participation. If the investigator decides to discontinue the study drug, refer to the study drug taper directions in the Study drug, Dose and Mode of Administration section.

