#### **4.4 Reproductive Potential**

##### **4.4.1 Female Contraception**

Sexually active females of childbearing potential should be using an acceptable form of contraception. Females of childbearing potential must be advised to use acceptable contraceptives throughout the study period and for 30 days after the last dose of study drug. If hormonal contraceptives are used, they should be administered per the package insert.

Females of childbearing potential who are not currently sexually active must agree to use acceptable contraception, as defined below, if they become sexually active during the period of the study and 30 days after the last dose of study drug.

Female subjects should be:

- Postmenopausal (12 consecutive months of spontaneous amenorrhea and  $\geq$  age 51 years), *or*
- Surgically sterile (having undergone one of the following surgical acts: hysterectomy, bilateral tubal ligation, bilateral oophorectomy, or bilateral salpingectomy) and at least 6 weeks post-sterilization, *or*
- Should have specimens collected prior to study drug initiation. If not possible then, collected as soon as possible after study drug initiation. Enrollment is not contingent upon results. However, if a subject has a positive test result, it will be at the investigators discretion to weigh the risks verses benefits for the subjects continued participation.

Acceptable methods of contraception are:

- Intrauterine device plus condoms
- Double-barrier methods (e.g., condoms and diaphragm with spermicidal gel or foam)
- Hormonal contraceptives (oral, patch, injectable, or vaginal ring), stabilized for at least 30 days prior to the study participation, plus condoms. Note: If subject becomes sexually active during the study, they should use one of the other acceptable methods noted above in addition to the hormonal contraceptive until it has been stabilized for 30 days.

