### **7.1.1 Screening Period**

#### **7.1.1.1 Screening**

Potential subjects are anticipated to be identified in emergency departments and/or hospital in-patient units. Upon identification, subjects will be screened for inclusion/exclusion criteria prior to receiving ganaxolone IV solution as adjunctive therapy.

Procedures specific to this protocol and not otherwise considered standard of care, will not be performed until written informed consent from the subject/parent/guardian/LAR has been appropriately obtained. Consent for subjects who are at risk for SE may be obtained prior to an SE event, this is also referred to as pre-consenting. Additional details on consent can be found in Section 10.3.1.

A screen failure is a subject who has given informed consent and failed to meet the inclusion criteria and/or met at least one of the exclusion criteria and has not been administered the study drug. Subjects cannot be rescreened once they have been designated as a screen failure per incidence of SE. Subjects who fail the screening but are not treated with ganaxolone IV solution may be rescreened if they face a new SE event.

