#### Pregnancy Test

As described in Table 1 and Section 4.4, a urine or serum pregnancy test should be collected for all females of childbearing potential prior to study drug initiation, and if pregnancy is suspected. If not possible to collect pre-dose, then collect as soon as possible after study drug initiation. It is at the sites' discretion whether to perform a urine or serum pregnancy test. Enrollment is not contingent upon results. However, if a subject has a positive test result, it will be at the investigators discretion to weigh the risks verses benefits for the subjects continued participation. If the investigator decides to discontinue the study drug, please refer to Section 4.5.

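### Exclusion criterion 6 and the pregnancy-test instructions give conflicting eligibility rules for a positive result known before study drug starts

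*Protocol*

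**What the plan says.** Two sets of current protocol text bear on this.

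**Eligibility.** Section 4.2 opens with "Subjects are excluded from the study if any of the following exclusion criteria are met", and criterion 6 reads "Subjects known or suspected to be pregnant upon screening". The Synopsis repeats the criterion in identical words. No exception is attached in either place. Section 7.1.1.1 counts as a screen failure a consented subject who "met at least one of the exclusion criteria and has not been administered the study drug". Section 10.2.2 makes the investigator responsible for enrolling only eligible subjects.

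**Testing.** Table 1 ticks the pregnancy test in the Screening column only. Footnote i says that the sample "should be collected pre-dose (screening). If not possible to collect pre-dose, collect as soon as possible after start of study drug infusion". Section 4.4.1 has the same timing: "Should have specimens collected prior to study drug initiation. If not possible then, collected as soon as possible after study drug initiation". Synopsis item 7 and Section 7.2.3.5 agree. Each of these four places then says "Enrollment is not contingent upon results" and asks the investigator, if the test is positive, "to weigh the risks verses benefits for the subjects continued participation" (wording of Section 7.2.3.5; the others differ only trivially). Section 8.1.6 repeats the discretion sentence without the enrollment sentence.

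**The concern.** The test is meant to be done before dosing, inside the screening period. A positive result at that point is the most direct way for a subject to become known, or at least suspected, to be pregnant at screening. Criterion 6 then excludes her. The testing instructions say that the result does not decide enrollment and hand the matter to the investigator. A site holding a positive result before the bolus therefore finds two instructions that point in opposite directions.

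What is at stake is the clarity of an eligibility rule that concerns possible fetal exposure. Decisions here are made under time pressure, since the Synopsis allows screening to last only a few minutes, and a site has little opportunity to ask which sentence governs.

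**Working it through.** No arithmetic applies. The point depends on no rate, effect size, alpha or sample size, so the check is to set the passages side by side.

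1. **Does a pre-dose result fall within screening?** Yes. Table 1 footnote a says "The screening period is from the time parent/guardian/LAR consent is obtained to immediately prior to study drug initiation". Anything known before the bolus is known at screening.

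2. **Does a positive pre-dose result meet criterion 6?** Yes. It makes the subject at least suspected to be pregnant, and meeting any one criterion is enough to exclude.

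3. **Does the enrollment sentence reach a pre-dose result?** As written, yes. In all four places it follows an instruction that covers both pre-dose and post-dose collection, and it carries no limit to late or pending results. It refers to the results themselves, not to whether they are available yet. In Synopsis item 7 and footnote i, one sentence governs the drugs-of-abuse test and the pregnancy test together. No exclusion criterion names a positive drug screen, so for that test the sentence naturally means that a positive does not bar entry. Nothing signals a narrower meaning for the pregnancy test.

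4. **Where do the rules collide?** Taking the possible cases in turn:

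| Test status at study drug initiation | Criterion 6 | Testing instructions | Conflict? |
|---|---|---|---|
| Negative result in hand | Not met on the test | Entry does not depend on the result | No |
| Sample not taken, or result pending, and no other reason to suspect pregnancy | Not met | Entry does not depend on the result | No |
| Result first available after dosing, positive | Looks back to screening; not met then | Investigator discretion on staying in the study | No |
| Positive result in hand before dosing | Met: excluded, screen failure | Entry does not depend on the result; investigator discretion | **Yes** |

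5. **Does the SAP settle it?** No. The schedule in SAP Appendix 1 (footnote l) repeats the testing wording from protocol Amendment 3 without adding a limit.

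6. **Does it affect any analysis?** SAP Section 4.1 defines Screened, Safety and Pharmacokinetic populations. Safety membership depends on having received ganaxolone, so a dosed subject is in it whichever rule is applied. SAP Section 4.7 lists violations for that population. SAP Section 4.8 summarises efficacy in it without inferential tests. No set definition and no planned estimate turns on this point.

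**The case against.** The strongest reply is that the two rules can be read together: criterion 6 governs what is known or suspected at screening, and the enrollment sentence means only that dosing need not wait for a result. There is real support for this. The sentence follows the fallback for samples that could not be taken before dosing. The discretion wording speaks of a subject staying in the study. In the Synopsis, footnote i and Section 7.2.3.5 the next step is stopping study drug, with a pointer to the taper directions or to Section 4.5, which suits a subject already dosed. Section 8.1.6 uses the discretion sentence in a section that counts pregnancies from the first dose. In status epilepticus, not delaying treatment for a test result is an understandable aim.

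This reading is plausible and may be what was intended, but the text does not state it. Section 4.4.1 carries the enrollment sentence with no mention of stopping study drug, and read literally all four places include a positive result obtained before dosing.

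The reply does succeed against two stronger conclusions that a reader might draw:

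- **That a site could either enrol or exclude such a subject and be compliant both ways.** The documents do not support this. Sections 4.2, 7.1.1.1 and 10.2.2 make the exclusion list the formal test of eligibility, and none of the testing passages says that it waives criterion 6.
- **That the SAP check for eligibility violations could not be applied.** It could. SAP Section 4.7 works from the inclusion and exclusion criteria. Criterion 6 is one of them and the testing sentence is not, so a dosed subject with a positive pre-dose result would be flagged under criterion 6 and listed.

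**Conclusion.** The point holds as an internal contradiction of limited reach. For a positive pregnancy test known before study drug initiation, the protocol gives an exclusion rule in Section 4.2 and the Synopsis criteria, and a contrary statement in Synopsis item 7, Table 1 footnote i, Section 4.4.1 and Section 7.2.3.5. For results first available after dosing there is no contradiction.

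The number affected is likely to be small: a woman of childbearing potential, a positive test, and a result returned before the bolus in an emergency setting. The documents give no expected count. The SAP now covers only the open-label part, planned at up to approximately 30 subjects. Sample size, power, alpha, analysis set definitions and estimates are untouched. The reason to correct it is that it is a safety-related eligibility rule and the correction is cheap.

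The conclusion assumes that the enrollment sentence is read as written. If the sponsor intended only that dosing need not wait for a result, the defect is a missing limit in the wording, and the same edit cures it.

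**What to change.** Reconcile the passages. Sections 4.2, 4.4.1 and 7.2.3.5, the Synopsis (criterion 6 and item 7) and Table 1 footnote i should state, in the same wording, (a) which rule applies to a positive result available before study drug initiation and (b) which applies to a result that arrives after it. Check Section 8.1.6 for consistency, and carry the agreed wording into the schedule footnote in SAP Appendix 1 if that appendix is kept. The choice of rule in each case is a clinical decision for the sponsor, and none is proposed here.

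The cost is a wording change in the protocol. No new data collection or analysis is needed.

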#### **4.3 Restrictions**

Subjects must abstain from the use of alcohol and from consuming grapefruit, Seville oranges, starfruit, or citrus-derived products until completion of the study.

Females who are breastfeeding will be encouraged to "pump and dump" for the duration of study participation and for 45 days after the last dose of study drug.

#### **4.4 Reproductive Potential**

##### **4.4.1 Female Contraception**

Sexually active females of childbearing potential should be using an acceptable form of contraception. Females of childbearing potential must be advised to use acceptable contraceptives throughout the study period and for 30 days after the last dose of study drug. If hormonal contraceptives are used, they should be administered per the package insert.

Females of childbearing potential who are not currently sexually active must agree to use acceptable contraception, as defined below, if they become sexually active during the period of the study and 30 days after the last dose of study drug.

Female subjects should be:

- Postmenopausal (12 consecutive months of spontaneous amenorrhea and  $\geq$  age 51 years), *or*
- Surgically sterile (having undergone one of the following surgical acts: hysterectomy, bilateral tubal ligation, bilateral oophorectomy, or bilateral salpingectomy) and at least 6 weeks post-sterilization, *or*
- Should have specimens collected prior to study drug initiation. If not possible then, collected as soon as possible after study drug initiation. Enrollment is not contingent upon results. However, if a subject has a positive test result, it will be at the investigators discretion to weigh the risks verses benefits for the subjects continued participation.

Acceptable methods of contraception are:

- Intrauterine device plus condoms
- Double-barrier methods (e.g., condoms and diaphragm with spermicidal gel or foam)
- Hormonal contraceptives (oral, patch, injectable, or vaginal ring), stabilized for at least 30 days prior to the study participation, plus condoms. Note: If subject becomes sexually active during the study, they should use one of the other acceptable methods noted above in addition to the hormonal contraceptive until it has been stabilized for 30 days.

